Official title: Treatment of acute exacerbations of chronic obstructive pulmonary disease with acupuncture during hospitalization: a three-arm double-blinded randomized sham-controlled trial

NCT number: NCT03398213

Date of the document: June 3, 2020

Methods:

Study design: This is a three-arm 1:1:1 randomized-controlled trial evaluating the efficacy and safety of the addition of acupuncture to SOC as compared to sham-procedure added to SOC (sham-control) and to SOC only (SOC-control) for treatment of AECOPD in patients hospitalized in internal medicine departments. The study protocol was reviewed and approved by the Institutional Review Board (IRB) in accordance with the Helsinki Declaration (0108-17-BNZ) and registered at www.clinicaltrials.gov (NCT03398213). Trial methods and results were reported according to the Consolidated Standards of Reporting Trials (CONSORT) 2010 guidelines.¹⁹

Participants: Patients hospitalized in internal medicine departments with a previous diagnosis of COPD³ were evaluated by department physicians. Inclusion criteria included a previous diagnosis of COPD and a clinical diagnosis of AECOPD as defined by the GOLD criteria.³ Exclusion criteria included hemodynamic instability, a platelet count below $20 \times 10^9/L$, expected respiratory deterioration requiring mechanical ventilation in the next 24 hours, or an inability to provide informed consent. Primary socio-demographic and medical data were recorded and compared between the three study groups.

Setting: The study was set in internal medicine departments of Bnai Zion medical center, a tertiary hospital in Haifa, Israel.

Interventions: The intervention protocol was based on a literature review and the Delphi process. A panel of eight acupuncturists of at least 5 years of experience in treating hospitalized patients were consulted. The experts were asked to review and analyze the literature regarding Traditional Chinese Medicine (TCM) and COPD, delineate relevant TCM syndromes and associated "critical" acupoints and treatment frequency. Their suggestions were based on literature data and their professional experience. Finally, three cycles of stepwise anonymous discussions were taken to obtain a consensus on the treatment approach. The conclusion was to

assign the patients into three groups for four daily consecutive treatment sessions and a 4-day follow-up.

Standard-of-care (SOC) only: Patients received SOC for AECOPD according to a standard protocol based on the GOLD guidelines.³ Such therapy included oxygen to maintain saturation around 90%, inhalations, antibiotics and systemic corticosteroids for five days. Noninvasive or mechanical ventilation were added depending on the severity of the AECOPD, as determined by clinical evaluation and blood gases.

True acupuncture + SOC group: Acupuncture treatment was documented according to STRICTA guidelines.²⁰

- Acupuncture rationale: The acupuncture was performed in a TCM style. During the Delphi process, a list of acupoints relevant to acute lung conditions were determined and associated with different TCM syndromes. Practitioners systematically documented syndrome diagnosis according to TCM reasoning and used only acupoints appearing in the list and corresponding to the TCM diagnosis.
- Details of needling: During the treatment, the acupuncturists used 75% alcohol pads to sterilize the skin around the acupoints. Subsequently, sterile disposable needles were inserted in the acupoints. An average of five Eco FDA-approved needles of 3-cm length and 0.22-mm diameter were inserted. The puncture depth varied with anatomical location from 0.5 to 1 cm. Manual needle stimulation was performed, but *de qi* sensation (e. g. dullness, sourness, heaviness, tingling sensation around the needle) was not sought.
- Treatment regimen: Four daily consecutive 15-20-minute sessions were administered.
- Other components of treatment: Patients in this group also received SOC as described earlier. No other complementary medicine therapies were added. Explanations were given to patients on potential benefits and side effects of acupuncture and treatment was administered only after they signed informed consent.
- Practitioner background: The treatment was administered by eight acupuncturists with at least 5 years of clinical experience in a hospital setting.
- Control intervention: The two control groups were SOC only (SOC-control) and SOC with sham-procedure (sham-control).

Sham-procedure + SOC group: Department physicians underwent a one-hour training on placing plasters on ear-points that have no relevance to lung conditions. During this training,

they were taught they are actually treating patients by stimulating ear acupoints and that the aim of the study was to compare the efficacy and safety of acupuncture administered by an experienced acupuncturist as compared to acupressure administered by unexperienced medical staff after a short training. Patients were told they are receiving ear-point stimulation. Therefore, this study arm was double blinded. SOC was administered as well as described earlier.

Outcomes:

The primary outcome was dyspnea intensity pre- and post-treatment in the 4 days of follow-up. It was measured daily, before and one hour after treatment (for acupuncture and sham-control groups) or after first evaluation (for SOC-control group), via the modified Borg (mBorg) scale, which is a validated scale that has been used to evaluate the degree of dyspnea (0- no dyspnea, to 10- worse dyspnea) in both stable COPD and AECOPD.^{21,22} Dyspnea intensity was chosen as primary outcome since it has been shown to predict clinical outcomes in AECOPD.²³

Secondary outcomes included:

Variation of clinical symptoms: Including cough intensity and sputum production associated with the AECOPD, as evaluated on a Visual Assessment Scale from 0 (no symptom) to 10 (maximally symptomatic), throughout the 4 days of evaluation.

Variation of physiologic features: Venous blood gases (pH and pCO₂) and oxygen saturation were measured before intervention and daily in the four evaluation days. Respiratory rate (RR) was measured daily, before and one hour after treatment (for true acupuncture and sham-control groups) or after first evaluation (for SOC-control group).

Treatment failure: Defined as death during hospitalization or need for noninvasive or mechanical ventilation. Treatment failure incidence was evaluated and compared between the three groups.

Duration of hospitalization: Evaluated and compared between the three study arms.

Safety: Acupuncture-related side effects were systematically evaluated after treatment in the true acupuncture group via the validated Acup-AE questionnaire administered to the patient by the acupuncturist immediately after therapy.²⁴

Minimal sample size: In a previous study evaluating the efficacy of acupuncture vs sham-acupuncture in 68 patients with chronic COPD (34 patients in each group), a 3.6±1.9 units improvement in dyspnea (according to mBorg scale) was found in the acupuncture arm, as

compared with a 0.4 ± 1.2 units improvement in the sham-acupuncture arm.⁸ According to these data and ANOVA test with alpha of 0.05 and an 80% power, we calculated a minimal sample size of 66 patients (22 in each group) for the current study.

Randomization: Patients meeting inclusion/exclusion criteria were randomized to either SOC with acupuncture (true acupuncture), SOC with sham-procedure (sham-control) or SOC only (SOC-control) using 1:1:1 permuted block randomization. The permuted block randomization list was generated by Excel software. To guarantee allocation concealment, randomization was done by an independent research assistant who did not participate in any other parts of the research and assigned the group code to each participant according to the randomization list. The independent research assistant was blinded to the meaning of the group code.

Blinding: Data collectors, department physicians, physicians administering the sham-procedure and the statistician were blinded to the group allocation status; acupuncturist blinding is clearly not possible, however, contact time with patients was the same in both true acupuncture and sham-control arms (15-20 min). Patients receiving both true acupuncture and sham-procedure were told they are treated for their respiratory condition by acupuncture/acupressure. The group allocation status was revealed after completion of the study.

Statistical analysis: Demographic and clinical data was analyzed at baseline to measure the balance among the study groups. Quantitative variables were described using mean \pm standard deviation or median and 25th-75th percentiles (Q1, Q3) depending on their distribution. Qualitative variables were described using frequency and percentage distributions. Next, we showed that our variables distribute equally between the study groups. For comparing normally distributed variables between our study groups, we used the ANOVA test. For comparing variables that do not distribute normally between our study groups, we used the Kruskal-Wallis test with adaptation to pairwise comparison. For comparing qualitative variables between our study groups, we used the independent Chi-square test and Fisher exact test. Bonferroni adjustment was used for multiple comparisons for each independent comparison of true acupuncture vs sham-control, true acupuncture vs SOC-control and sham-control vs SOC-control. Since the variation of dyspnea intensity between day 1 and day 2 had a normal distribution, a multivariate linear regression analysis was performed after collinearity, interaction and confounding analysis, in order to neutralize the effect of the different sociodemographic and medical covariates on the primary outcome in the 3 study arms. The adjusted unstandardized regression coefficients were given with confidence interval (CI), while

a $p < 0.05$ was considered as statistically significant. Data analysis was performed using IBM SPSS version 22 statistics software.

Results:

Baseline patient data: 104 patients were screened for eligibility from November 2017 to February 2020. Among them, 72 met inclusion criteria and were recruited. Twenty-six of them were assigned to the true acupuncture arm, 24 to the sham-control arm, and 22 to the SOC-control arm. Baseline demographic and clinical characteristics were similar in patients from the 3 study arms as shown in Table 1. To note, all the patients randomized to any of the three groups completed treatments per-protocol (Fig. 1).

Primary outcome: Baseline dyspnea was similar in the three groups. A statistically significant difference between the three groups in dyspnea intensity was found from the first day of evaluation after treatment (median [Q1, Q3] mBorg score 5.0 [4.0, 5.0] in true acupuncture, 6.0 [4.25, 7.875] in sham-control and 7.5 [5.5, 8.0] in SOC-control, $p=0.014$ – significant difference of both true acupuncture vs sham-control: $p=0.031$, and true acupuncture vs SOC-control: $p=0.014$, but non-significant between sham-control and SOC-control: $p=0.34$), and until day 3 after treatment (Fig. 2A). After adjustment for such covariates in a multivariate linear regression analysis, the association of study arm with improvement of dyspnea from day 1 to day 2 remained statistically significant (Table 2).

Secondary outcomes:

- Patient-reported outcomes:

Baseline VAS scores for cough and sputum intensity were similar in the three study arms (Table 1). No statistically significant difference in the cough intensity was observed between the three study arms throughout the 4 days of follow-up (Fig. 2). However, a statistically lower level of sputum production was observed in the true acupuncture arm as compared with sham-control and SOC-control from day 2 ($p=0.04$) (Fig. 2). Post-hoc analysis showed a statistically significant difference between true acupuncture and sham-control in day 2 ($p=0.024$), day 3 ($p=0.010$) and day 4 ($p=0.018$), while only on day 2 between true acupuncture and SOC-control ($p=0.044$), and no statistically significance between sham-control and SOC-control.

- Physiologic assessment:

Baseline physiologic data were similar in the three groups (Table 1). A statistically significant difference was observed in respiratory rate (RR) at day 2 after treatment ($p=0.002$), with significant difference both between true acupuncture and sham-control ($p=0.005$) and between true acupuncture and SOC-control ($p=0.003$), but not between sham-control and SOC-control

($p=0.050$), while all other RR measurements were statistically similar between the 3 arms throughout the 4-day follow-up (Fig. 3A).

Concerning pH, a statistically significant difference was observed at day 4 between the 3 groups ($p=0.048$), although post-hoc analysis did not show any statistical significance when comparing groups head-to-head (Fig. 3C).

No statistically significant difference was observed when comparing other physiologic measures between the 3 study groups (Fig. 3).

- *Treatment failure:*

No death or mechanical ventilation occurred in the study participants during follow-up. However there had a total of 4 treatment failures, all of them were non-invasive ventilations, which occurred in 2 (8%) patients in the true acupuncture arm, 1 (4.3%) in the sham-control arm and 1 (5%) in the SOC-control arm ($p=0.83$).

- *Duration of hospitalization:*

No difference was noted in terms of duration of hospitalization between the three study arms (5.5 ± 2.3 days for true acupuncture vs. 6.0 ± 2.9 days for sham-control and 6.3 ± 2.9 days for SOC-control, $p=0.050$).

- *Safety:*

No side effect of acupuncture treatment was reported during the study period as assessed by the Acup-AE questionnaire.

Tables and Figures:

Table 1: Baseline characteristics

[figure not shown]
Characteristics	True acupuncture (N=26)	Sham-control (N=24)	SOC-control (N=22)	p
Age (mean ± SD)	69.2±10.1	70.7±8.1	67.4±9.3	0.47
Gender (Men)	20 (77%)	15 (62%)	17 (77%)	0.43
Comorbidities				
Cardiovascular	18 (69%)	20 (83%)	15 (68%)	0.42
Respiratory (other than COPD)	7 (27%)	2 (8%)	5 (23%)	0.23
Gastroenterological	2 (8%)	4 (17%)	5 (23%)	0.34
Renal / Urologic	7 (27%)	3 (12%)	5 (23%)	0.44
Metabolic / Endocrinological	15 (58%)	13 (54%)	13 (59%)	0.94
Hematological / Oncological	3 (12%)	6 (25%)	3 (14%)	0.40
Neurological	4 (15%)	0 (0%)	1 (5%)	0.09
Smoking status				
Smoker	13 (50%)	16 (67%)	14 (64%)	0.44
Former smoker	13 (50%)	8 (33%)	8 (36%)	
Never smoked	0	0	0	
CCI (median [Q1, Q3])	6.0 [3.5, 6.0]	5.0 [4.0, 6.75]	4.5 [3.0, 7.25]	0.87
COPD severity				
Mild: FEV1 ≥ 80%	1 (4%)	0 (0%)	1 (5%)	
Moderate: 50% ≤ FEV1 < 80%	4 (15%)	5 (21%)	5 (23%)	0.69
Severe: 30% ≤ FEV1 < 50%	7 (27%)	11 (46%)	9 (41%)	
Very severe: FEV1 < 30%	5 (19%)	4 (17%)	4 (18%)	
Unknown	9 (35%)	4 (17%)	3 (14%)	
Pulmonary hypertension				
None	10 (38%)	15 (62%)	16 (73%)	
Mild: mPAP = 25-40 mmHg	4 (15%)	3 (12%)	3 (14%)	
Moderate: mPAP = 41-55 mmHg	3 (12%)	0	2 (9%)	0.11
Severe: mPAP > 55 mmHg	0	0	0	
Unknown	9 (35%)	6 (25%)	1 (5%)	
COPD exacerbation hospitalizations				
0	19 (73%)	12 (50%)	9 (41%)	
1-4	6 (23%)	11 (46%)	9 (41%)	0.09
≥5	1 (4%)	1 (4%)	4 (18%)	
Treatment				
Inhalations	24 (92%)	23 (96%)	22 (100%)	0.41
Systemic corticosteroids	3 (12%)	3 (13%)	1 (5%)	0.61
Theophylline	0	0	1 (5%)	0.32
Oxygen home therapy	8 (31%)	12 (52%)	8 (36%)	0.29
BiPAP	4 (15%)	2 (8%)	4 (18%)	0.60
APACHE-II at admission (mean ± SD)	13.3±3.6	12.0±4.4	11.0±3.8	0.14
Baseline data (median [Q1, Q3])				
Dyspnea (mBorg)	8.0 [5.5, 8.75]	6.5 [5.0, 8.5]	7.75 [6.0, 8.5]	0.82
Cough (VAS)	7.5 [5.0, 8.0]	5.0 [5.0, 7.4]	5.0 [3.6, 7.5]	0.35
Sputum (VAS)	6.0 [1.5, 7.5]	6.0 [4.25, 6.0]	5.0 [1.9, 6.0]	0.22
O₂ saturation				
≤ 80%	4 (15%)	1 (4%)	0	0.30
81-89%	9 (35%)	10 (42%)	10 (45%)	
≥ 90%	13 (50%)	13 (54%)	12 (55%)	
PCO₂ (mmHg)				
< 45	6 (23%)	3 (12%)	8 (36%)	
45-60	12 (46%)	17 (71%)	9 (41%)	0.10
60-80	5 (19%)	4 (17%)	5 (23%)	
> 80	3 (12%)	0	0	
pH				
< 7.2	0	0	0	
7.2-7.3	5 (19%)	4 (17%)	1 (5%)	0.30
> 7.3	21 (81%)	20 (83%)	21 (95%)	
Respiratory rate (/min) (median [Q1, Q3])	21 [16, 23.75]	22 [16.5, 26]	20 [16, 22]	0.26

Legend: CCI: Charlson Comorbidity Index; mPAP: Mean Pulmonary Arterial Pressure; SOC: Standard-Of-Care.

Table 2: Multivariate linear regression analysis on variation of dyspnea from day 1 to day 2

Factors and covariates	Adjusted unstandardized coefficient (B)	95% Confidence interval		p value
		Inferior	Superior	
Constant (Intercept)	2.088	-3.409	7.584	0.457
Study Arm				
True acupuncture	2.172	0.421	3.923	0.015
Sham-control	0.390	-1.319	2.099	0.655
SOC-control	0	-	-	-
Cardiovascular comorbidities (0=No, 1=Yes)	-0.322	-2.935	1.391	0.713
Gastroenterological comorbidities (0=No, 1=Yes)	4.703	2.527	6.879	<0.001
Hospitalizations for COPD in the last year	-0.379	-0.756	-0.003	0.048
Age	-0.040	-0.133	0.053	0.400
APACHE-II	0.118	-0.099	0.336	0.287
Charlson Comorbidity Index	-0.026	-0.406	0.354	0.894

Figure 1: Flow-chart

Legend: SOC: Standard-of-care.

Figure 2: Between-group comparison of patient-reported outcomes

[figure not shown]

Figure 3: Between-group comparison of physiologic features

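### Four-day dyspnea is tested day by day with no rule for discharge; one repeated-measures model should carry the conclusion, because day 3-4 readings may be incomplete

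*Combined protocol and SAP*

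**What the plan says.** The Outcomes section sets the window: "The primary outcome was dyspnea intensity pre- and post-treatment in the 4 days of follow-up". The score is taken each day, before and one hour after the session, or after the first evaluation in the SOC-only arm. Interventions gives the matching schedule, which is to "assign the patients into three groups for four daily consecutive treatment sessions and a 4-day follow-up". The physiologic measures follow the same calendar: "Venous blood gases (pH and pCO₂) and oxygen saturation were measured before intervention and daily in the four evaluation days". Participants and setting are internal medicine inpatients. No section describes a reading after discharge.

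Statistical analysis names ANOVA, Kruskal-Wallis and chi-square or Fisher tests between arms, and a linear regression on the change in dyspnea from day 1 to day 2. Results then reports significance day by day. There is no rule for missing readings or for discharge before day 4.

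Three other statements bear on the point:

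- Duration of hospitalization: "5.5 ± 2.3 days for true acupuncture vs. 6.0 ± 2.9 days for sham-control and 6.3 ± 2.9 days for SOC-control".
- Baseline patient data: "Twenty-six of them were assigned to the true acupuncture arm, 24 to the sham-control arm, and 22 to the SOC-control arm", and "all the patients randomized to any of the three groups completed treatments per-protocol".
- True acupuncture group, treatment regimen: "Four daily consecutive 15-20-minute sessions were administered".

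**The concern.** A ward-based reading on day 4 needs a patient who is still on the ward. With mean stays of 5.5 to 6.3 days and SDs of 2.3 to 2.9, a four-day window reaches well into the lower part of the distribution of stay. If readings end at discharge, and discharge tends to follow improvement, the patients compared on days 3 and 4 would no longer be the full randomized groups. A separate test on each day uses whoever has a reading that day. It does not use the earlier scores of those who have gone.

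The results exposed are the dyspnea difference on day 3 and its absence on day 4, sputum for acupuncture versus sham on days 3 and 4 (p=0.010 and p=0.018), and pH on day 4 (p=0.048). The day-1 dyspnea comparison (p=0.014) and the day 1-2 regression in Table 2 come from days when nearly all patients should still be present.

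**Working it through.** **Inputs.** Stay 5.5±2.3, 6.0±2.9 and 6.3±2.9 days (Duration of hospitalization). Arms of 26, 24 and 22, total 72 (Baseline patient data).

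**The plan's own figure.** The only stated result built on these inputs is p=0.050 for stay. One-way ANOVA from the summaries:

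- Grand mean = (26×5.5 + 24×6.0 + 22×6.3)/72 = 5.911.
- Between-arm mean square = 7.91/2 = 3.96.
- Within-arm mean square = (25×2.3² + 23×2.9² + 21×2.9²)/69 = 502.29/69 = 7.28.
- F = 0.54, p = 0.58. The most favourable rounding of every input gives p of about 0.49.

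So p=0.050 is not reproduced by ANOVA. A Kruskal-Wallis test on the raw data cannot be checked. The line needs checking before much is built on it.

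**Share of short stays.** For mean m, SD s and cut-off c:

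- Normal: Φ((c−m)/s).
- Lognormal: Φ((ln c − μ)/σ), with σ² = ln(1+s²/m²) and μ = ln m − σ²/2.
- Gamma: shape (m/s)², scale s²/m.

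Example, acupuncture, normal, c=4: Φ((4−5.5)/2.3) = 0.257, and 0.257×26 = 6.7 patients.

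| Stay below | Shape | Acupuncture | Sham | SOC | All 72 |
|---|---|---|---|---|---|
| 4 days | normal | 25.7% | 24.5% | 21.4% | 17.3 (24.0%) |
| 4 days | lognormal | 27.7% | 25.6% | 20.7% | 17.9 (24.8%) |
| 4 days | gamma | 28.1% | 26.8% | 22.4% | 18.7 (25.9%) |
| 3 days | normal | 13.9% | 15.0% | 12.8% | 10.0 (13.9%) |
| 3 days | lognormal | 9.5% | 10.0% | 7.0% | 6.4 (8.9%) |
| 3 days | gamma | 12.1% | 13.2% | 10.2% | 8.5 (11.9%) |

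**Which cut-off applies.** The documents give neither the time origin of the stay nor the enrolment day. A patient enrolled on the admission day who stays three nights can still give a day-4 reading, so the cut-off for day 4 would be 3 days. Enrolment a day after admission could move it to 5 days, about 37% under the normal shape. For a day-3 reading with same-day enrolment the cut-off is 2 days, which gives 7.2% (normal), 3.1% (gamma) or 1.1% (lognormal). The day-3 exposure is thus smaller than the day-4 exposure.

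**Can nobody have left before 4 days?** Yes. These whole-day samples with a minimum of 4 match the stated figures:

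- Acupuncture (26): fifteen stays of 4, three of 5, then 6, 7, 8, 9, 9, 9, 10, 11. Sum 144, mean 5.54; sum of squares 928, SD = √((928−144²/26)/25) = 2.28. Skew is about 1.2.
- Sham (24): twelve of 4, then 5, 5, 6, 6, 6, 7, 7, 8, 10, 11, 12, 14. Mean 6.04, SD 2.93.
- SOC (22): ten of 4, then 5, 5, 6, 7, 7, 8, 8, 8, 9, 10, 13, 13. Mean 6.32, SD 2.90.

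The lowest share consistent with the stated means and SDs is therefore 0%.

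**Difference between arms.** Below 4 days, acupuncture exceeds sham by 1.2 to 2.1 points and SOC by 4.3 to 7.0 points, or at most about two patients. Below 3 days the order of acupuncture and sham reverses in all three shapes.

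**Completeness elsewhere.** The sham treatment-failure rate is 1 (4.3%). 1/23 = 4.35% and 1/24 = 4.17%, so the denominator was 23. Home oxygen in Table 1, 12 (52%), is also 12/23 = 52.2%, not 12/24 = 50%. At least one sham patient is missing from some counts, one of them at baseline, so this says nothing about discharge.

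**The case against.** The strongest objection is that the document addresses presence directly. It says every randomized patient completed treatment, and that four sessions were given in the acupuncture arm. Read literally, nobody in the two treated arms left before the fourth session. A share modelled from a mean and SD cannot override that, and the samples above show that the two can be reconciled. A 4-day floor needs marked right skew if the excess is modelled as gamma (2.5 to 3.1), but the acupuncture sample above needs only 1.2, and a 3-day floor needs only ordinary skew. Reporting stay as mean and SD, when the plan allows that "or median and 25th-75th percentiles (Q1, Q3) depending on their distribution", is weak evidence against such shapes and does not exclude them. The flow chart and the figures with daily results are also not visible in the text available, and numbers per day may stand there.

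Most of this stands. A reader might infer that about a quarter of patients had gone by day 4, that late results rest on a remainder selected by recovery, or that acupuncture lost more good responders and that this explains the loss of significance after day 3. The documents support none of these as fact. The share is model-based, discharge following improvement is an assumption, and the modelled gap between acupuncture and sham is about one to two points and changes sign with the cut-off.

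What the objection does not remove is narrower. Completing treatment is not the same as having every reading. In the SOC-only arm there was no study session, so the completion statement cannot settle whether its day 3-4 readings exist. The analysis still has no stated way to handle a patient who leaves.

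**Conclusion.** The point holds as a possible risk together with a weakness in the analysis. It is not a demonstrated bias. A four-day primary outcome in inpatients is analysed by separate daily tests and a regression that stops at day 2, with no discharge rule. Under ordinary shapes, roughly 9-26% of patients (about 6 to 19 of 72) would have stays below 3 to 4 days; the documents' own figures are also consistent with none.

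The affected results are day-3 dyspnea, day 3-4 sputum and day-4 pH, with day 3 less exposed than day 4. Day-1 dyspnea and the day 1-2 regression are largely untouched. Differential loss between arms is not shown.

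The size rests on three assumptions: stay is counted in days from admission, enrolment fell at or soon after admission, and the stated means and SDs are correct. The unreproduced p=0.050 leaves the last of these open.

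**What to change.** Analyse all daily mBorg readings in one repeated-measures model with arm, day, arm-by-day interaction and baseline dyspnea (the day-1 reading before the session), marking whether each later reading precedes or follows the session. Keep every randomized patient with any reading after baseline. Base the four-day dyspnea conclusion on this model in place of the separate daily tests. If a patient's departure depends on scores already recorded, the model uses those scores; a test on the remaining patients does not.

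Support it with:

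- the number observed per arm at each occasion, with the reason for each missing reading;
- the time origin of the stay and the enrolment day relative to it, and a check of the p value for stay;
- reconciliation of the completion statement with the stays, and of the sham denominator of 23 with the 24 assigned;
- a label on blood gases and respiratory rate as inpatient-only, if any patient had left.

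The cost is one model and one table on data already collected. The downside is the modelling assumption: missing at random, and approximate normality of a 0-10 score. A sensitivity analysis can check both, by varying the assumed dyspnea of patients who left and by repeating the comparison with a rank-based method. Telephone symptom readings after discharge can serve only a future trial.

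### Cough, sputum and the physiologic outcomes are called 'variation' without a definition and compared as unadjusted daily levels, so the baseline already collected goes unused

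*Combined protocol and SAP*

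**What the plan says.** **Definition.** Under Outcomes, the symptom entry reads "Variation of clinical symptoms: Including cough intensity and sputum production associated with the AECOPD", scored 0 to 10 "throughout the 4 days of evaluation". The physiologic entry reads "Variation of physiologic features: Venous blood gases (pH and pCO₂) and oxygen saturation were measured before intervention and daily in the four evaluation days", and respiratory rate is added before and after each session. Neither entry says what is subtracted from what, or over which interval.

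**Analysis.** The Statistical analysis section does use the word with an interval, for dyspnea: "Since the variation of dyspnea intensity between day 1 and day 2 had a normal distribution". Table 2 then models that change. For other outcomes the section gives ANOVA if normal and otherwise this: "For comparing variables that do not distribute normally between our study groups, we used the Kruskal-Wallis test with adaptation to pairwise comparison". The only covariate-adjusted model is the regression "on the primary outcome in the 3 study arms", which is dyspnea.

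**Results.** For cough: "No statistically significant difference in the cough intensity was observed between the three study arms throughout the 4 days of follow-up". For sputum: "a statistically lower level of sputum production was observed in the true acupuncture arm", stated against both controls from day 2. Respiratory rate is reported as different at day 2 and pH at day 4. No change score, trajectory or baseline term appears. The text calls baseline cough and sputum similar, with p=0.35 and p=0.22 in Table 1.

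**The concern.** The name of the outcome points to movement from a starting value, and the analysis looks only at where patients stood on each day. With arms of 26, 24 and 22, chance can leave the starting values apart, and the cough medians in Table 1 are apart. A test of daily levels that ignores the starting value then mixes any treatment effect with the part of the baseline gap that persists. It also leaves in the residual the variation that the baseline could explain.

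The secondary conclusions are at stake: a null for cough, a positive finding for sputum, and isolated time-point findings for respiratory rate and pH. The sputum text has a separate problem. It first claims a lower level than both controls from day 2, and the next sentence confines the SOC difference to day 2.

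**Working it through.** **Inputs from Table 1**, median [Q1, Q3]:

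| | Acupuncture (26) | Sham (24) | SOC (22) | p |
|---|---|---|---|---|
| Cough | 7.5 [5.0, 8.0] | 5.0 [5.0, 7.4] | 5.0 [3.6, 7.5] | 0.35 |
| Sputum | 6.0 [1.5, 7.5] | 6.0 [4.25, 6.0] | 5.0 [1.9, 6.0] | 0.22 |

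The baseline-to-follow-up correlation, rho, is not given. I assume 0.3 to 0.7.

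**1. The plan's own figure.** I rebuilt cough data from the quartiles, with an assumed minimum of 0 to 3 and maximum of 9 to 10. Kruskal-Wallis then gives p of about 0.12 to 0.24. That is not 0.35, but ties and tails are unknown, so it neither confirms nor refutes the printed value.

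**2. Size of the cough gap.** The median gap is 7.5 − 5.0 = 2.5 against each control. The carry-over formula in step 3 works on means, so I approximate these as (Q1 + median + Q3)/3:
- Acupuncture: (5.0 + 7.5 + 8.0)/3 = 6.83
- Sham: (5.0 + 5.0 + 7.4)/3 = 5.80
- SOC: (3.6 + 5.0 + 7.5)/3 = 5.37

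The mean gap is about 1.03 against sham and 1.47 against SOC. Standard deviations from the quartiles are 2.35, 1.89 and 3.09, pooled 2.47. The approximate 95% intervals are −0.4 to 2.4 and 0.0 to 2.9.

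**3. Part carried into follow-up levels**, rho × baseline gap (equal standard deviations assumed):

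| rho | vs sham | vs SOC |
|---|---|---|
| 0.3 | 0.31 | 0.44 |
| 0.5 | 0.52 | 0.73 |
| 0.7 | 0.72 | 1.03 |

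All of it runs against acupuncture. For scale, suppose the follow-up standard deviation is also 2.47. The standard error for 26 vs 24 is 2.47 × √(1/26 + 1/24) = 0.70. The difference detectable with 80% power is then about 2.0 points, or 2.3 at the Bonferroni level. The shift against sham is therefore about 0.31/1.96 = 16% to 0.72/1.96 = 37% of the unadjusted detectable difference.

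**4. Precision.** Relative to raw levels, and with equal standard deviations, the variance is 1 − rho² for ANCOVA and 2(1 − rho) for an unadjusted change score:

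| rho | ANCOVA | Change score |
|---|---|---|
| 0.3 | 0.91 | 1.4 |
| 0.5 | 0.75 | 1.0 |
| 0.7 | 0.51 | 0.6 |

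At rho = 0.5, adjusting 72 patients is worth 72/0.75 = 96 unadjusted ones. This is a linear-model figure and only a guide for rank tests.

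**5. Sputum.** Approximate means are (1.5 + 6.0 + 7.5)/3 = 5.0 for acupuncture, (4.25 + 6.0 + 6.0)/3 = 5.4 for sham and (1.9 + 5.0 + 6.0)/3 = 4.3 for SOC. The baseline tilts slightly in favour of acupuncture against sham (0.4) and against acupuncture relative to SOC (0.7).

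**6. Sputum wording.** The opening sentence claims a lower level than both controls from day 2 (p=0.04). The post-hoc sentence gives sham p=0.024, 0.010 and 0.018 on days 2, 3 and 4, and SOC p=0.044 on day 2 only. The claim against SOC after day 2 is not supported by the text that follows it.

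**The case against.** The strongest reply is that nothing was switched. 'Variation' is a heading label with no formula, the stated window is the whole four days, and a course over days fits daily reporting. Where the document means a difference, it names the interval. That stands: the defect is an undefined term, and a reader who infers that a defined change endpoint was replaced goes further than the text. The reply does not rescue the analysis, because separate tests on each day do not estimate a course over time either.

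Second, comparing post-randomization levels is legitimate, and an unadjusted change score is noisier than levels when rho is below 0.5. Both points stand. Moreover, ANCOVA of change and ANCOVA of level give the same arm effect once baseline is a covariate: Y − B = a + tT + bB rearranges to Y = a + tT + (b + 1)B, with t unchanged. So the substance is the missing baseline term, not level versus change.

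Third, Table 1 shows p=0.35 and overlapping quartiles. The overlap is real and shrinks the gap. But a non-significant baseline test in arms of this size is no reason to leave out a measured starting value.

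Fourth, the baseline argument is shown mainly for cough. Respiratory rate medians were 21, 22 and 20 (p=0.26). That stands. For the physiologic outcomes the case is precision and consistency, not a demonstrated tilt.

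Fifth, the post-hoc sputum sentence already gives the correct pattern. So the reader can recover it, but the opening sentence still overstates it.

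**Conclusion.** The point holds as one of undefined terms and missing baseline adjustment in the secondary outcomes. For cough, the uncorrected imbalance is worth about 0.3 to 0.7 points against sham and 0.4 to 1.0 against SOC, to the disadvantage of acupuncture. This rests on quartile-based means, equal standard deviations and an assumed rho of 0.3 to 0.7. Figures 2 and 3 are not readable here, so it also rests on the Results text.

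Three stronger readings are tempting and not supported:
- *Acupuncture patients started 2.5 points worse, shifting the comparison by 0.75 to 1.75 points.* The 2.5 is a gap between medians, and the shift formula needs means.
- *Cough fell further with acupuncture, and the null hides it.* No significant difference is not equality, and no follow-up cough values are readable. The documents cannot show that the result would change.
- *The sputum finding against SOC is flattered by the lower SOC baseline.* The direction is the reverse: acupuncture started higher (median 6.0 vs 5.0).

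The primary dyspnea result is untouched.

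**What to change.** 1. State for each secondary outcome what 'variation' means: which values are compared, and over which interval.
2. For cough, sputum, respiratory rate, pH, pCO₂ and oxygen saturation, add an analysis with the pre-treatment day-1 value as covariate. This can be ANCOVA, rank ANCOVA or proportional odds where the distribution requires it, or a repeated-measures model across the days. Report between-arm estimates with confidence intervals.
3. Label this analysis post hoc and print it beside the existing level comparisons, which stay.
4. Reword the sputum result as lower than sham on days 2 to 4 and lower than SOC on day 2 only.

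The cost is a re-run on data already collected and some rewording. Some secondary p-values may move in either direction. Because the adjusted analysis is chosen after the results are known, it supports the existing findings or qualifies them but does not supersede them.
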